## 2.10.2 Exit Survey

Using Study ID#, Progressive will send an email to study participants with a link to an exit survey hosted by TrueMotion approximately 3-7 days before the end of the intervention period. This survey will elicit feedback from participants about their experience in the study and how the intervention impacted their behavior surrounding phone use while driving.

## 2.11. Assessment Controls

Participants allocated to the control arm that have iPhones will receive push notifications prompting them to enable Do Not Disturb While Driving once a week for 3 weeks, without receiving any feedback or goal support for the intervention period, 50 days.

## 2.12. Outcomes Assessment and Blinding

The primary outcome will be seconds of active handheld, non-call use per hour of driving. Research associates and investigators will be blinded to the allocation until outcome evaluation. It is not possible to blind subjects given the nature of the intervention. We do not expect any scenarios where emergency unblinding will be necessary.

## **2.13. Compensation**

Participants will be compensated \$10 for completing the intake survey and \$10 for completing the End of Study Survey. Arms 3-6 will receive compensation based on their driving scores. Participants will be scored based on historical demographic data that has been split into 3 buckets: 1) low performers (<50%); 2) average performs 50-89%; 3) top performers >90%.

## **2.14. Regulatory**

[figure not shown]
This study is IRB exempt. The Penn research team will not receive any PHI or identifiable information and all trial procedures and participant payments will be conducted and dispersed by TrueMotion. The trial is minimal risk to participants, given that the only possible risk will be from potential breach of confidentiality. TrueMotion will not have identifiable information of participants other than email address for communication and study payments. Regarding user driving data, Progressive will send a global unique identifier (GUID) to TrueMotion. TrueMotion will pair those GUIDs with those that have enrolled into the study. This way, TrueMotion will not have name/demographic data of participants connected with their Progressive Snapshot driving data. TrueMotion will send the list of enrolled GUIDS to Progressive. Only Progressive will have demographic information regarding which of their participants have enrolled into the study. Participants will voluntary provide their email address to TrueMotion to receive compensation.

The study has been registered on clinicaltrials.gov under NCT03833219

## **2.15. Contingencies and Participant Withdrawal**

If a participant withdraws from the study, further communication will be stopped. Data collected prior to withdrawal will be maintained but additional data will not be collected.

## 2.16. Study Flow Diagram

## 3. OUTCOMES

### 3.1. Definitions

#### 3.1.1. Primary Outcome

**Seconds of active handheld phone use per hour of driving.** This is a composite outcome that measures the proportion of total trip time in which the customer is engaged in handheld phone call use or non-call handheld use (e.g. texting, swiping, and typing) as measured by the Snapshot mobile application. Several studies (e.g. Klauer, *NEJM*, 2014) have demonstrated the association between handheld phone use, such as reaching for phone, typing, swiping, dialing, and increased crash risk. This outcome is also known as the **active phone use percentage**. Passive phone use (e.g. phone is streaming GPS navigation directions or music without any typing, swiping, and handheld holding of the phone) is not included in this outcome. Customers are able to view their active phone use percentage for each trip in the Snapshot Mobile app. Trips are only counted if the Snapshot Mobile app predicts the customer was a driver for the trip based on the phone sensor data. In the Snapshot Mobile program, customers can open the Snapshot app and reclassify trips from driver trips to passenger trips and vice versa for up to 5 days. This outcome is currently not used to calculate future auto-insurance rates and discounts among eligible study participants.

### 3.1.2. Secondary Outcomes - Effectiveness

**Seconds of active handheld call use per hour of driving.** We will analyze the components of the primary outcome separately.

**Seconds of active handheld non-call use per hour of driving.** We will analyze the components of the primary outcome separately.

**Hard breaking events per 100 miles.** This is measured by the Snapshot Mobile app, reported for each trip, and used to calculate future auto-insurance rates and discounts.

**Fast acceleration events per 100 miles.** This is measured by the Snapshot Mobile app, reported for each trip, and used to calculate future auto-insurance rates and discounts.

### 3.1.3. Secondary Outcome 2 – Cost Effectiveness

**Incremental Cost-Effectiveness Ratio.** We will measure the incremental cost-effectiveness of the intervention arms relative to the control arm and to each other. This will be done by calculating incremental cost-effectiveness ratios as follows:

$$[(\text{Incentive Costs in Intervention Arm}) - (\text{Incentive Costs in Comparison Arm})] / [(\text{Seconds of active handheld use / hour of driving in Intervention Arm}) - (\text{Seconds of active handheld use / hour of driving in Comparison Arm})]$$

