## **2. TRIAL DESIGN**

### **2.1 Overview**

We propose to conduct a randomized, control trial evaluating the comparative effectiveness of social comparison and financial incentive interventions with customers of Progressive's mobile phone usage-based insurance policy. A total of 3,000 adult participants will be enrolled with 500 participants per arm. We expect an attrition rate of 17% based on historical customer data.

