## **2.9. Allocation to Treatment**

Progressive Snapshot users that opt-in to participate will be added to a study list tracked by TrueMotion. 3,000 participants have enrolled into the study, they will complete an intake survey, collecting information about driving history, demographics, and behavioral characteristics. Simple individual-level randomization will be used. TrueMotion will use a random number generator to randomize each user that opts in to 1 of the 6 arms: (Arm 1) control, (Arm 2) social comparison feedback, (Arm 3) end of rating period incentive, (Arm 4) end of rating period incentive and social comparison feedback (Arm 5) weekly loss framed incentive and social comparison feedback, (Arm 6) larger weekly loss framed incentive and social comparison feedback. Intervention will be delivered by TrueMotion through the Snapshot mobile app to the study participants. Additionally, iPhone users in all arms will get push notifications prompting them to activate the Do Not Disturb While Driving setting on iPhones.

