## B. Final Statistical Analysis Plan

### 1. STATISTICAL ANALYSIS PLAN

#### 1.1. Analytic Methods

The primary outcome is **seconds of active handheld phone use per hour of driving**, which can also be expressed as active phone use %. We will use fractional regression with a logit link function as our primary analytic model to assess effectiveness between and among the 5 interventions. Specifically, we will evaluate these 10 predefined contrasts:

1. Social Comparison Feedback versus Control (monitor only)
2. End of Rating Period Incentive versus Control (monitor only)
3. End of Rating period Incentive + Social Comparison Feedback versus Control (monitor only)
4. Weekly Loss-Framed Incentive + Social Comparison Feedback versus Control (monitor only)
5. Larger Weekly Loss-Framed Incentive + Social Comparison Feedback versus Control (monitor only)
6. End of Rating Period Incentive versus Social Comparison Feedback
7. End of Rating Period Incentive + Social Comparison Feedback versus Social Comparison Feedback
8. End of Rating Period Incentive + Social Comparison Feedback versus End of Rating Period Incentive
9. Weekly Loss-Framed Incentive + Social Comparison Feedback versus End of Rating Period Incentive + Social Comparison Feedback
10. Larger Weekly Loss-Framed Incentive + Social Comparison Feedback versus Weekly Loss-Framed Incentive + Social Comparison Feedback

Although longitudinal models such as generalized estimating equations might be considered in light of the repeated trip measures among individual participants, fractional regression with a logit link is preferred in this case because the primary outcome collapses to a proportion between 0 and 1 that is weighted by travel time within and across trips. Furthermore, weekly feedback messages and incentives are delivered based on the weekly averages of seconds of active handheld phone use time divided by weekly total trip time. The model will be adjusted for: 1) length of time in the Snapshot program during the Baseline period; 2) and observed primary outcome during the Baseline period. Other covariates to be included in the model include:

1. Proposed baseline covariates to be included in primary outcome analysis model
2. Baseline period active phone use % (i.e. total active handheld phone use seconds / total trip seconds)
3. Proportion of period active phone use % due to handheld calls vs. handheld non-call use
4. Mean hours of driving/week during baseline period
5. Age
6. Sex
7. Marital status

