These estimates should be conservative as adding the rich set of baseline covariates (e.g. demographics, Apple Car Play, etc) to the model should increase the precision of the model estimates.

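### As written, the cost-effectiveness ratios divide by an unadjusted difference in arm rates and so forgo the precision of the baseline-adjusted primary model

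*Combined protocol and SAP*

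**What the plan says.** Protocol section 3.1.3 defines the ratio as the difference in incentive costs divided by the difference in seconds of handheld use per hour of driving. The effect term is "Seconds of active handheld use / hour of driving in Intervention Arm" minus the corresponding rate in the comparison arm. No baseline value, covariate or model is named. The scope is wide: "We will measure the incremental cost-effectiveness of the intervention arms relative to the control arm and to each other".

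Final SAP section 1.1 treats the same outcome differently: "We will use fractional regression with a logit link function as our primary analytic model". The model is adjusted for time in the Snapshot program, "observed primary outcome during the Baseline period" and a list of further covariates. Section 1.2 of the SAP expects that adding baseline covariates "to the model should increase the precision of the model estimates". The final SAP has no cost-effectiveness section, so nothing there says which estimate feeds the ratio.

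On allocation, protocol section 2.9 states: "Simple individual-level randomization will be used". Section 2.1 sets the size: "A total of 3,000 adult participants will be enrolled with 500 participants per arm".

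**The concern.** Simple randomisation does not balance baseline phone use by design, so arms will differ on it by chance. The primary model removes the part of the outcome difference that this explains. A plain difference in arm rates keeps it.

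The loss matters more in a ratio than in a simple difference, because a ratio is unstable when its denominator is near zero. That is most likely between two active arms with similar effects, and section 3.1.3 asks for those comparisons. At stake is a value-for-money ordering of similar arms that is noisier than it need be and may differ by chance from the ordering in the primary analysis.

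**Working it through.** **Which ratios are affected.** Six arms give 6 × 5 / 2 = 15 pairs. Only arms 3 to 6 carry incentive costs (protocol 2.10.1 and 2.13). Arm 2 versus arm 1 is therefore $0 − $0 over the effect, which is zero for any non-zero denominator. At most 14 ratios are affected. SAP 1.1 has 10 contrasts, so five pairs (5 v 2, 6 v 2, 5 v 3, 6 v 3, 6 v 4) have no primary contrast to set beside the ratio.

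**Inputs.** No cost-effectiveness figure is stated, so there is none to reproduce. No SD is given either, so the standard error must be backed out of the power statement in SAP 1.2: 52 s/h detectable with power 0.80 at 3,000 participants. Two assumptions are needed: two-sided alpha 0.05 and 500 analysed per arm. The correlation ρ between baseline and intervention-period use is also not given and is varied from 0.3 to 0.8. Equal variances in the two periods and a linear approximation to the fractional logit model are assumed.

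**Unadjusted standard error.** 52 / (1.960 + 0.842) = 18.6 s/h. The implied SD is 18.6 / √(2/500), about 293 s/h.

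Cross-checks:
- The 401 per arm for 60 s/h in protocol 4.2, read the same way, gives SD = 60 × √(401/2) / 2.802 = 303 s/h and a standard error of 19.2 s/h at 500 per arm.
- If the calculation used alpha 0.005, the standard error would be 52 / (2.807 + 0.842) = 14.3 s/h.
- The power statements do not fully agree. A standard error of 18.6 gives power of about 0.90 at 60 s/h, not the stated 0.94. The standard error is therefore approximate.

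**Adjusted standard error** = 18.6 × √(1 − ρ²). **Noise from chance baseline imbalance** in the unadjusted difference = ρ × 18.6. **Wrong-sign probability** = Φ(−true difference / SE), shown for an assumed true difference of 20 s/h.

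| | SE (s/h) | Imbalance noise SD (s/h) | Variance removed | Wrong sign at 20 s/h |
|---|---|---|---|---|
| Unadjusted | 18.6 | – | – | 14% |
| ρ = 0.3 | 17.7 | 5.6 | 9% | 13% |
| ρ = 0.5 | 16.1 | 9.3 | 25% | 11% |
| ρ = 0.7 | 13.3 | 13.0 | 49% | 7% |
| ρ = 0.8 | 11.1 | 14.8 | 64% | 4% |

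At a true 20 s/h, unadjusted and adjusted differences have opposite signs in about 9%, 12% and 13% of simulated trials (ρ = 0.5, 0.7, 0.8).

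**At the planned effect sizes.** The unadjusted wrong-sign probability is Φ(−52/18.6) ≈ 0.25% at 52 s/h and Φ(−60/18.6) ≈ 0.06% at 60 s/h. What remains is the spread of the ratio. With the cost difference held fixed and a true 60 s/h, a ±1.96 SE error multiplies the ratio by:
- unadjusted: 60/(60 + 36.4) = 0.62 to 60/(60 − 36.4) = 2.54;
- adjusted, ρ = 0.7: 60/(60 + 26.0) = 0.70 to 60/(60 − 26.0) = 1.76.

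**The case against.** **The formula does not say unadjusted.** Section 3.1.3 is an outcome definition, and model-standardised arm means in s/h would also fit it. This stands in part. A difference of arm rates is the plain reading, but it is a reading. On the other reading the estimator is unspecified, and the same sentence settles it.

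**Unadjusted differences are legitimate.** Randomisation keeps them unbiased. A reader might infer that chance imbalance biases the ratios, or distorts all of them. The documents support neither: the loss in the denominator is precision only, and arm 2 versus control is zero regardless.

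**The primary analysis promises no difference in s/h.** A reader might infer that the trial will report two conflicting effect sizes for each contrast. SAP 1.1 specifies a logit-link model and p-values for contrasts, not an adjusted difference in s/h, and five pairs have no primary contrast. That inference fails. What remains is that the ratio is not tied to the adjusted analysis.

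**20 s/h is a favourable choice.** It is well below the planned 52 s/h, where any ratio is fragile. This stands: sign reversal is a problem only for similar arms. With alpha 0.005 (standard error 14.3) the unadjusted 14% becomes 8%.

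**Costs move with baseline too.** Payouts depend on the level of phone use (protocol 2.13). An arm with lighter users by chance shows a larger apparent reduction and also higher payouts, which partly offset in a ratio against control. Adjusting only the denominator gives up that offset. The mechanism is real but small. In a simulation of an end-of-period incentive arm against control (true effect 60 s/h, ρ = 0.7, normal outcomes), payout noise was about 4% of mean cost, against 18.6/60 = 31% in the denominator. Adjusting the denominator alone narrowed the central 95% of the ratio from about $0.2–0.7 to about $0.2–0.5 per s/h avoided. Treating cost and effect consistently is still the better plan.

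**Conclusion.** The point holds as one of precision. Read plainly, section 3.1.3 uses an unadjusted denominator although the planned primary model could supply a more precise one. The variance saved ranges from 9% (ρ = 0.3) to 64% (ρ = 0.8). For effects of 52 to 60 s/h the direction of the denominator is safe either way, with a wrong sign in at most about 0.3% of trials, and the gain is a tighter ratio. Between active arms about 20 s/h apart, adjustment cuts the wrong-sign probability from about 14% to between 13% and 4%, and an ordering that differs from the primary analysis is possible.

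All of these sizes rest on an assumed alpha, 500 analysed per arm, the assumed range of ρ and, for the last, an assumed 20 s/h. Severity is minor: the ratio is a secondary outcome with no test, threshold or decision rule, and the primary conclusions do not depend on it.

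**What to change.** In protocol section 3.1.3, or in a short cost-effectiveness section of the SAP, state three things:

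1. The denominator is the covariate-standardised marginal difference in s/h from the fractional logit model of SAP 1.1: the average predicted rate under each arm, taken over all participants. The model coefficient is a log odds ratio and cannot be used directly.
2. Because payouts also depend on the level of phone use, mean incentive cost in the paying arms is standardised over the same baseline covariates.
3. The version from unadjusted arm rates and costs is shown as descriptive.

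No new data are needed, and the effect term comes from a model already planned. The cost is slightly more analysis and a ratio that is no longer built from simple arm averages.

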### 3.1.4. Secondary Outcome 3 - Acceptability

Acceptability of interventions will be measured using a mixed-methods approach:

**Snapshot Mobile app notifications disabled.** Given the eligible participants will have notifications enabled, if a customer disables notifications, this could indicate a lack of acceptability of push notification interventions.

**Net promoter score.** In the exit survey, participants will be asked “*How likely is it that you would recommend the intervention you received to a friend or colleague?*” on a 0 to 10 scale.

**Responses to open-ended questions in exit survey.** Participants will be asked the following two open-ended questions: 1) “Please tell us what you *liked* about participating in this study;” 2) “Please tell us what *didn't like* about participating in this study and how we should improve the experience in the future.” These qualitative responses will be coded for content related to intervention acceptability and emerging themes will be identified by randomization arm.

## 4. STATISTICAL ANALYSIS PLAN

### 4.1. Analytic Methods

The primary outcome is **seconds of active handheld phone use per hour of driving**, which can also be expressed as active phone use %. We will use logistic regression as our primary analytic model to assess effectiveness between and among the 5 interventions. Specifically, we will evaluate these 10 predefined contrasts:

1. Social Comparison Feedback versus Control (monitor only)
2. End of Rating Period Incentive versus Control (monitor only)

3. End of Rating period Incentive + Social Comparison Feedback versus Control (monitor only)
4. Weekly Loss-Framed Incentive + Social Comparison Feedback versus Control (monitor only)
5. Larger Weekly Loss-Framed Incentive + Social Comparison Feedback versus Control (monitor only)
6. End of Rating Period Incentive versus Social Comparison Feedback
7. End of Rating Period Incentive + Social Comparison Feedback versus Social Comparison Feedback
8. End of Rating Period Incentive + Social Comparison Feedback versus End of Rating Period Incentive
9. Weekly Loss-Framed Incentive + Social Comparison Feedback versus End of Rating Period Incentive + Social Comparison Feedback
10. Larger Weekly Loss-Framed Incentive + Social Comparison Feedback versus Weekly Loss-Framed Incentive + Social Comparison Feedback

Although longitudinal models such as generalized estimating equations might be considered in light of the repeated measures among individual participants, logistic regression is preferred in this case because the primary outcome collapses to a number between 0 and 1. The model will be adjusted for: 1) length of time in the Snapshot program program during the Baseline period; 2) and observed primary outcome during the Baseline period.

Due to the multiple pre-planned contrasts, we will adjust for multiple comparisons using the Holm method. First, the 10 contrasts will be ranked (lowest to highest) based on the raw p-value from the logistic regression. For a contrast to be significant using the Holm threshold, the raw p-value must be below the threshold for each row calculated as  $(0.05 / [\text{In remaining constraints}])$ . Correspondingly, for clarity of presentation, adjusted p values will be reported by multiplying the raw p value by the number of remaining contrasts. For example, the smallest p-value is multiplied by 10 to obtain the adjusted p-value.

#### **4.2. Sample Size, Power, and Minimum Detectable Differences**

To detect a clinically meaningful reduction of 60 seconds/hour of driving (i.e. an absolute reduction in phone use % of 1.67%), the minimum sample size is 2,406 (401 per arm).

With a target sample size of 3,000 and power of 0.80, we should be able to detect a difference between treatment arms of 52 seconds/hour of driving (i.e. an absolute reduction in phone use % of 1.44%). We would have a power of 0.94 to detect a difference of 60 seconds/hour of driving.

These estimates should be conservative as adding the rich set of baseline covariates (e.g. demographics, Apple car play, etc) to the model should increase the precision of the model estimates.

#### **4.3. Subgroup Analyses and Effect Modification**

For the 10 pre-defined contrasts, we will also assess the effect modification of having an iPhone versus Android phone. This will enable us to estimate the effectiveness of push notifications to enable automated activation of Do Not Disturb While Driving. These notifications only get sent to iPhones.

### **5. DATA COLLECTION AND MANAGEMENT**

#### **5.1. Data Collection Process**

All study data, including survey data and driving data will be the collected by TrueMotion and demographic data will be collected by Progressive. All baseline and outcome variables will be obtained prospectively

from elective surveys or through the Snapshot App maintained by TrueMotion. Penn researchers will not collect any study data and will receive de-identified data to analyze outcomes.

## **5.2. Variables**

Measure library is included in the Appendix

## **5.3. Data Quality and Validity**

Data quality and validity will be optimized by using a detailed data dictionary which will be distributed to TrueMotion. Data quality will be monitored by the TrueMotion development and tech team.

## **5.4 Transfer of Data**

Study data, including survey data and driving data will be de-identified (email address removed) and transferred to the UPenn research via an encrypted .csv file uploaded to a secure, cloud based data storage system hosted on PMACs servers. The file will be password protected and the password will be provided to the research team via telephone.

Demographic data from Progressive will be transferred in the same manner.

Demographic data will be matched with study data using a study ID # assigned to each participant.

